In Phase II, for participants randomized to the treatment arm, if the participant does not complete the post-intervention assessments within 2 weeks from the end of the intervention period they will be considered lost to follow up. If a participant chooses to withdraw from the study at any point or the participant is deemed lost to follow up or is dropped from the study during the intervention period (5 weeks), access to the web portal and mobile app will be restricted at that time, otherwise access to the mobile app will be restricted at the end of the intervention period and access to the web portal will be restricted after post-intervention assessments have been completed or the participant is deemed lost to follow up (2 weeks after intervention period).

Participants randomized to the control arm will have two weeks to complete the post-intervention assessments. Once the post-intervention assessments have been completed or 2 weeks have passed, whichever occurs first, participants in the control arm will be granted access to the treatment condition (Limbix Spark) for 5 weeks. After access to Limbix Spark for 5 weeks, participants will have two weeks to complete another set of post-intervention assessments. If a participant chooses to withdraw from the study or the participant is deemed lost to follow up during the control app intervention period or Limbix Spark app intervention period (5 weeks

each), access to the web portal and mobile app will be restricted at that time. Otherwise, access to the mobile app will be restricted at the end of each intervention period and access to the web portal will be restricted after the second set of post-intervention assessments have been completed or the participant is deemed lost to follow up (2 weeks after Limbix Spark intervention period).

In Phase II, if participants report a change in their treatment for a mental health disorder while enrolled in the study, they may be withdrawn from the study.

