In Phase II, all participants will be compensated \$25 in the form of an electronic gift card for completing the baseline assessments and \$25 for completing each set of post-intervention assessments regardless of adherence to intervention (1 set of post-intervention assessments will be completed if assigned to the treatment arm and 2 sets of post-intervention assessments will be completed if assigned to the control arm-- 1 after completing the control app and another after subsequently completing the Limbix Spark app.) Gift cards will be emailed to participants.

If participants indicated during the consent process that they would be interested in participating in a post-intervention feedback interview, a research coordinator may contact participants and their legal guardian (if under 18) to set up this interview to be conducted over video conferencing. Participants who were randomized to the control condition may be contacted to complete these interviews following completion of the control arm, prior to starting the treatment condition. Participants and their legal guardian will be asked, separately, to answer questions about their experience with the program and provide feedback that may help improve the product for future users. These interviews may be audio-recorded with permission. These interviews are expected to take 1 hour, and participants and parent/legal guardians who participate will be compensated \$25/hr. Reimbursement will be prorated for interviews lasting less than 1 hour. For participants randomized to the control arm in Phase II, this interview will occur after completion of the Limbix Spark intervention period.

All relevant FDA requirements for the conduct of clinical trials will be followed, including registration on [clinicaltrials.gov](http://clinicaltrials.gov).

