### **3.4 Assessments**

Baseline and post-intervention assessments for participants and parents (if under 18) will be completed via a secure web portal. Weekly participant assessments will be completed in the mobile app. Weekly parent assessments will be completed via secure web portal.

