###### Phase II

- Between-subjects treatment-related change in depressive symptoms from baseline to 5-weeks as measured by PHQ-8 for those with baseline PHQ-8  $\geq 10$ .

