## Phase II

The main purpose of Phase II is to evaluate the effectiveness of the Limbix Spark program relative to an educational control condition. All analyses will be restricted to those participants with PHQ-8  $\geq 10$  unless otherwise indicated. Data from participants who reported a change in their medication or treatment for a mental health disorder that occurred during the study may be excluded from primary analysis. The core analysis strategy in this project is longitudinal mixed effects modeling, where we fully utilize the repeatedly measured primary and secondary outcomes and maximum likelihood estimation will be applied.

Data across versions 2 and 3 will be pooled and statistical analyses conducted with the combined dataset may be computed with version included as a covariate. Statistical analyses may also be conducted separately for versions 2 and 3 cohorts. All analyses will be completed in line with the intent-to-treat (ITT) principle, where all participants will be included in the analyses according to their assigned study arm at baseline, regardless of adherence to study protocol. Modern per protocol analyses will also be conducted to estimate treatment effects for participants who adhered to the protocol. All analysis results will be two-tailed, with a significance level at 0.05 and 95% confidence intervals.

All measures will be analyzed using mixed effects modeling, followed by generalized estimating equations to account for irregularly spaced measurements, fully utilizing all repeated measures and all available data. Missing data will be imputed using multiple imputation and likelihood-based analyses. Case analysis or single

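### Phase II plan permits excluding participants whose mental health treatment changes from the primary analysis, which would break the intent-to-treat analysis stated in the next paragraph

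*Combined protocol and SAP*

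**What the plan says.** Section 4.4 (Phase II) makes two statements about who is analysed. The first is a permission: data from participants who reported a change in medication or "treatment for a mental health disorder that occurred during the study may be excluded from primary analysis". The second, one paragraph later, applies intent-to-treat to all analyses: "all participants will be included in the analyses according to their assigned study arm at baseline", whatever their adherence. A further sentence adds a separate set: "Modern per protocol analyses will also be conducted to estimate treatment effects for participants who adhered to the protocol".

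The Phase II primary outcome in section 4.1 is "change in depressive symptoms from baseline to 5-weeks as measured by PHQ-8", in those with a baseline score of at least 10.

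Section 3.1 has a companion rule on conduct. If Phase II participants report "a change in their treatment for a mental health disorder while enrolled in the study, they may be withdrawn from the study". The Spark-arm paragraph treats withdrawal by choice, loss to follow-up and being dropped alike: where someone "is dropped from the study during the intervention period (5 weeks), access to the web portal and mobile app will be restricted", with immediate effect. The control-arm paragraph names withdrawal by choice and loss to follow-up, but not being dropped. Section 3.4 explains why access matters: "Baseline and post-intervention assessments for participants and parents (if under 18) will be completed via a secure web portal". The weekly participant PHQ-8 is completed in the app.

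**The concern.** A change of treatment happens after randomisation and may depend on both the assigned arm and how the participant is doing. Removing people on that basis can undo the comparability that randomisation gave. The plan names the trigger (a reported change) but not what kind of change is enough, who decides, when, or whether that person is blind to arm and outcome.

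Two features leave the choice open to influence by results. Section 4.4 analyses the primary outcome when 60 and again when 120 participants have completed. Section 3.4 places questions on treatment change in the Post-Program Questionnaire, in the same post-intervention set as the PHQ-8. Nothing prevents the exclusion being decided once these data have been seen.

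Two analysts who both follow section 4.4 could therefore report different primary results. The primary effect size may also be used to size Phase III (sections 2.1 and 4.4).

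**Working it through.** **1. Do the statements fit together?** The exclusion is tied by name to the primary analysis. The intent-to-treat sentence covers all analyses and all participants. Per-protocol analyses are listed separately, so the exclusion is not presented as that set, and nothing labels it a sensitivity analysis. No text says which statement governs. The restriction to baseline PHQ-8 of 10 or more is different in kind: it is measured before either program is used.

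**2. What happens to the data of someone who is withdrawn?** Withdrawal or dropping during the 5 weeks restricts portal and app access (section 3.1). The post-intervention PHQ-8 uses the portal and the weekly PHQ-8 uses the app (section 3.4). Later scores, including week 5, may therefore not be collected, whichever analysis rule applies. Weekly scores before withdrawal remain, and the mixed model can use them if they are not excluded. Participants who merely stop using the app are not affected: payment is for "completing each set of post-intervention assessments regardless of adherence to intervention".

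**3. Which period counts?** The exclusion refers to changes during the study, not during the 5-week primary period. From section 3.1:
- Spark: 5 weeks, plus up to 2 for assessments = 5 to 7 weeks.
- Control: 5 + up to 2 + 5 on Spark + up to 2 = 10 to 14 weeks (section 2.5 says up to 12).
- Ratio: from 10/7 = 1.4 to 14/5 = 2.8.

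Section 4.1 equally permits a 5-week reading, under which the windows are the same. The text does not choose.

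**4. Size.** The effect size comes from section 2.1, whose own figure reproduces: d = 0.5, two-sided 0.05 and 80% power need 64 per arm by t-test, and 128/0.73 = 175.3 against the stated 175. The documents give no rate of treatment change and no link to outcome, so everything below is assumed.

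Let severity have SD 1, with Spark 0.5 lower than control. In each arm exclude the fraction p with the highest propensity to change treatment, where propensity has correlation r with severity. With z the upper-p normal quantile and λ = φ(z)/(1-p), the retained mean shifts by -rλ and the retained variance is 1 - r²(zλ + λ²). For p = 5%, z = 1.645 and λ = 0.109; for p = 15%, z = 1.036 and λ = 0.274. Then d = mean difference / pooled retained SD, at 60 per arm:

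| Excluded, Spark / control | r | Mean difference | Pooled SD | d | Shift |
|---|---|---|---|---|---|
| 5% / 15% | 0.3 | 0.5 - 0.082 + 0.033 = 0.450 | 0.988 | 0.46 | -0.04 |
| 5% / 15% | 0.7 | 0.5 - 0.192 + 0.076 = 0.384 | 0.932 | 0.41 | -0.09 |
| 15% / 5% | 0.3 | 0.5 + 0.082 - 0.033 = 0.550 | 0.988 | 0.56 | +0.06 |
| 15% / 5% | 0.7 | 0.5 + 0.192 - 0.076 = 0.616 | 0.932 | 0.66 | +0.16 |

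With equal fractions in the two arms the mean shifts cancel and the difference stays at 0.5. A simulated mixed model (weekly scores, 400,000 per arm, 5-week window, 2-11% of control and 2-9% of Spark changing, change more likely after a high score) moved d by less than 0.01.

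**The case against.** The strongest defence is that the exclusion is only permitted. A conflict arises only if it is used, and the intent-to-treat sentence cannot be wholly literal, because the same section already restricts analyses by baseline score and speaks of adherence. The exclusion might then be a named exception. This stands in part: the accurate statement is that using the permission breaks the stated analysis, not that the primary analysis is already invalid. It does not remove the problem, because no text calls the exclusion an exception and the discretion is unbounded.

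A reader might infer more than the documents support:

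- *That the result will be biased for or against Spark.* No rate is given, section 2.5 requires two months of stable treatment at entry, and the sign depends on which arm changes more. Even the 15% versus 5% case moves d by less than its standard error at 60 per arm, √(2/60 + 0.5²/240) = 0.185.
- *That power is lost.* Section 3.1 says Phases I and II may not be powered. Nor is a loss automatic: removing the tail also shrinks the SD. In the model above, power with no exclusion is 77.5%. Equal exclusion of 2%, 5% or 10% gives 77.1%, 76.1% or 74.2% at r = 0.3, but 78.8%, 79.4% or 79.3% at r = 0.7.
- *That the control arm is certain to lose more people.* That needs the literal window; section 4.1 allows an equal one.
- *That all data on these participants vanish.* Earlier weekly scores survive, and a change first reported in the Post-Program Questionnaire need not come with a missing week-5 score.

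**Conclusion.** The concern holds on the text. Section 4.4 permits a discretionary exclusion after randomisation from an analysis that it also describes as including everyone as assigned, and section 3.1 may stop the week-5 score being collected from the same people. This conclusion needs no assumption about rates.

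The consequence for the estimate is not established in size or direction: near zero with equal 5-week windows, and -0.09 to +0.16 in d across the assumed 15% versus 5% cases. The figures rest on a normal model with correlation 0.3 to 0.7 and ignore truncation at baseline PHQ-8 of 10. They illustrate what could happen and do not predict it. This should be fixed, because the primary analysis set ought to be settled before outcomes are seen.

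**What to change.** - Delete the exclusion from the primary analysis. Include every randomised participant with baseline PHQ-8 of 10 or more, with all PHQ-8 data collected up to week 5, including scores after a treatment change.
- Make exclusion, or censoring at the change, a pre-specified sensitivity analysis that counts only changes up to week 5 in both arms. Use the date of change where it is recorded, and add a date field if it is not. Report changes by arm.
- Reconcile section 3.1 with section 4.4, using the same wording for both arms, so that the week-5 PHQ-8 is still requested after withdrawal where consent and the safety procedures (sections 4.5 and 4.5.1) allow. Who is withdrawn remains a clinical matter and is not changed.

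The cost is one amendment, which section 4.5.2 sends to the DSMB, possibly a date field, and a route for collecting the week-5 score once access is restricted. The downside is that the primary estimate then includes any effect of newly started treatment; the sensitivity analysis addresses that.

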## **2. Criteria for Subject Selection**

### **2.1 Number of Subjects**

A convenience sample of participants will be recruited via online advertising, social media, word of mouth, flyering, and recommendations by doctors, schools, and other youth and/or health-focused organizations. Limbix may also work with participant recruitment companies, such as TrialFacts and Dynata. Healthcare providers involved in identifying potential study participants may be compensated for recruitment efforts (based on hourly effort and not on number of referrals or enrolled participants). A total of 60 participants will be recruited in Phase I, and a minimum of 120 participants with PHQ-8  $\geq 10$  will be recruited in Phase II. A statistically powered Phase III study will be designed following completion of Phase II.

Preliminary power calculations revealed that a sample size of 175 will achieve 80% power to detect a moderate effect size (Cohen's  $d=0.5$ ) between Limbix Spark and active control at a significance level of 0.05 for a two-tailed t-test with an estimated 27% attrition rate. A moderate effect size is expected based on previous digital interventions with active controls for depression and evidence of superior efficacy for CBT-based interventions. An effect size will be calculated at the end of Phase II and may inform power calculations in determining sample size for Phase III.

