There will be two phases of this study. Phase I will evaluate feasibility of a minimum viable product (MVP) version of the Limbix Spark mobile app (Version 1) within the context of a real world deployment. After feasibility is established, Phase II will be initiated during which a primary outcome of effectiveness of the Limbix Spark app will be evaluated. At the commencement of Phase II, an updated version of Spark (Version 2) will be implemented. In order to quickly support teens during COVID-19 with an engaging and efficacious digital treatment, one additional app update is planned (Version 3) during Phase II. Recruitment for Phases I and II may not be powered to detect statistically significant differences between Spark and the educational control condition. Participants in Phase I will be randomized using a 1:1 ratio. Participants in Phase II will be randomized using a block randomization approach to ensure equal group sizes. Block size will range in multiples of 2 from 4-12 and be randomly generated to prevent guessing of allocation and eliminate bias.

In Phase I if the participant does not complete the post-intervention assessments within 4 weeks from the end of the intervention period they will be considered lost to follow up. If a participant chooses to withdraw from the study at any point or is deemed lost to follow up or dropped from the study during the intervention period (5 weeks), access to the web portal and mobile app will be restricted at that time. Otherwise, access to the mobile app will be restricted at the end of the 5-week intervention period and access to the web portal will be restricted after post-intervention assessments have been completed or the participant is deemed lost to follow up (4 weeks after intervention period). Participants will be compensated \$25 in the form of an electronic gift card or cash transfer for completing the post-intervention assessments regardless of adherence to their assigned intervention. Gift cards will be emailed to participants.

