imputation methods may also be used and a specific approach for imputation will be selected based on key attributes of the obtained data, including % missing and whether data are missing at random^109. Sensitivity analyses will be conducted to determine if data are missing at random. In these analyses, allowing for random intercepts and slopes, the change (slope) will be the key dependent variable and the randomization status will be the key independent variable. The results of these analyses can be easily converted to group or treatment differences at post assessments. In our mixed effects modeling, all variables will be analyzed as continuous with the exception of clinical concerns (occurrence/non-occurrence), which will be treated as a repeatedly measured binary outcome.

As an exploratory investigation, multiple variables will be investigated as possible moderators of treatment effects on depressive symptoms (PHQ-8). For example, we may evaluate medication status, symptom severity, age, sex, COVID19 specific factors, and aspects of program engagement (e.g., time to complete program, duration of use) as potential moderators. For this investigation, we will employ the MacArthur framework for moderator analysis, following the eligibility and analytical criteria for determining moderators. To maximize power, moderator analyses will also be conducted using mixed effects modeling.

Exploratory analyses using mixed effects modeling will also be conducted to evaluate whether successive program updates (between versions 2 and 3 of Limbix Spark) result in statistically significant differences on primary and secondary outcome measures, including depressive symptoms, global functioning, and treatment adherence, usability, and engagement.

Content analysis of post-study interviews will be conducted. Data will be codified to identify themes with an emphasis on engagement, usability, comprehension, therapeutic alliance, and overall impact of treatment. Key insights will be drawn from themes and contextualized with quantitative user session data.

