Lastly, we will assess treatment adherence by evaluating treatment-related differences in rates of program completion and daily mobile app usage using independent samples (between treatment and control groups) or paired (within the educational control group) t-tests. We will also assess treatment-related differences in self-reported usability and engagement using the SUS and UES scales descriptively by comparing means and variability between groups and within group (control group only)

Statistical analyses for the primary outcome variable and between group differences in rates of clinical concerns rates will be conducted when N=60 (~30/grp) and N=120 (~60/grp) participants have completed Phase II. If no statistical differences are detected in the primary outcome variable, possible moderators of treatment status on the primary outcome may be evaluated, including age, concurrent treatment, and PHQ-8 score at baseline. Results of the interim analyses may be used to adjust recruitment targets for the remainder of the trial.

An effect size will be calculated for the primary outcome and may be used to determine sample size for a Phase III trial.

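### Phase II mixed models: maximum likelihood with no stated small-sample degrees of freedom makes standard errors slightly too small (nominal 5% tests run at about 5.4–5.9% with 60 analysed, 5.2–5.4% with 120)

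*Combined protocol and SAP*

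**What the plan says.** Section 4.4 (Phase II) makes longitudinal mixed effects modelling the core strategy, "where we fully utilize the repeatedly measured primary and secondary outcomes and maximum likelihood estimation will be applied". The model is fitted "allowing for random intercepts and slopes, the change (slope) will be the key dependent variable and the randomization status will be the key independent variable", so the test of interest is the arm difference in slope. The same section states: "All analysis results will be two-tailed, with a significance level at 0.05 and 95% confidence intervals".

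Analyses of the primary outcome and of clinical concern rates "will be conducted when N=60 (~30/grp) and N=120 (~60/grp) participants have completed Phase II". The pooled analysis of app versions 2 and 3 "may be computed with version included as a covariate", and "Statistical analyses may also be conducted separately for versions 2 and 3 cohorts"; no cohort sizes are given. Generalized estimating equations (GEE) are to follow the mixed models, with no variance estimator named.

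The protocol does not mention restricted maximum likelihood (REML), a reference distribution for the mixed-model tests, a degrees-of-freedom method or a small-sample correction. The only reference to a t-test for the treatment effect on symptoms is in the sample-size paragraph of Section 2.1. The t-tests in Section 4.4 concern program completion and app usage.

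**The concern.** Full maximum likelihood (ML) estimates the between-person variance with divisor N and ignores the degrees of freedom spent on the fixed effects. The standard error of the arm-by-slope effect is therefore biased downward. A second small-sample error arises if the estimate divided by its standard error is referred to a normal distribution, which is the default in some mixed-model software. Both errors act in the same direction: intervals are too narrow and differences are declared slightly too often.

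The effect grows as the sample shrinks, so it matters most at the 60-participant look and in any separate version cohort. Section 4.4 makes further moderator analyses conditional on no difference being detected, and lets interim results change recruitment targets. An adjustment for repeated looks would not remove the error, because it lies in each test and interval.

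**Working it through.** **Inputs from the documents.** Looks at 60 and 120 participants who have completed Phase II; two-sided 0.05; random intercepts and slopes (all Section 4.4). Equal groups, from "Participants in Phase II will be randomized using a block randomization approach to ensure equal group sizes" (Section 3.1). 27% attrition (Section 2.1).

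**Assumptions.** Balanced, complete data for the exact formulas. The reference distribution is not stated, so results are shown for both t on N−2 degrees of freedom and Wald z.

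**The plan's own figure.** Section 2.1 gives 175 for d = 0.5, 80% power and 27% attrition. A two-sample t-test needs 63.77 per arm, rounded to 64, or 128 in total; 128/0.73 = 175.3. The figure is reproduced, and it rests on a t reference. The plan gives no type I error for the mixed model, so there is no such figure to reproduce.

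**Formula.** With balanced data and random intercepts and slopes, the arm-by-slope test is a two-sample t-test on each person's fitted slope. REML gives the usual standard error, and

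SE(ML)/SE(REML) = √((N−2)/N).

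The ML test rejects when |t(N−2)| > c·√((N−2)/N), where c is the t quantile or 1.96. At N = 60 the ratio is √(58/60) = 0.983. With c = 1.96 the effective critical value is 1.927, where the correct value is 2.002; P(|t(58)| > 1.927) = 5.9%. With c = 2.002 the effective value is 1.968, giving 5.4%.

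| Participants analysed | SE ratio ML/REML | ML, t reference | ML, z reference | REML, z reference | REML, t reference |
|---|---|---|---|---|---|
| 60 | 0.983 | 5.4% | 5.9% | 5.5% | 5.0% |
| 82 | 0.988 | 5.3% | 5.6% | 5.4% | 5.0% |
| 120 | 0.992 | 5.2% | 5.4% | 5.2% | 5.0% |
| 164 | 0.994 | 5.1% | 5.3% | 5.2% | 5.0% |

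**Why 82 and 164.** Section 4.4 counts participants who have completed and keeps everyone randomized under intention to treat. At 27% attrition, 60/0.73 = 82 and 120/0.73 = 164. Using the balanced formula at these sizes ignores the fact that dropouts contribute only part of their data.

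**Interval width relative to the correct interval.** With z: 1.927/2.002 = 0.963 at N = 60 (3.7% too narrow) and 0.981 at N = 120 (1.9%). With a t reference the shortfall is that of the standard error alone: 1.7% and 0.8%.

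**Simulation check.** ML and REML were fitted to six weekly visits with assumed variance components (random-intercept variance 9, slope variance 0.5, residual SD 2.5), 3,000 trials at N = 60 and 1,500 at N = 120. ML with z rejected in 5.4% at N = 60 with complete data and in 5.8% when 27% of the 60 dropped out. REML with t gave 4.8% and 5.0%. At N = 120 with dropout, ML with z gave 4.6% and REML with t 4.2%. The Monte Carlo standard error is about 0.4 points at 3,000 trials and 0.6 at 1,500, so the simulation agrees with the formulas but cannot resolve an excess of a few tenths of a point. The exact results carry the argument.

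**The case against.** The strongest reply is that the effect is very small and partly conditional, and most of that stands.

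- **ML alone adds little.** It adds 0.4 points at 60 analysed and 0.2 at 120. The 5.9% and 5.4% also need a Wald z reference, which the plan neither specifies nor rules out.
- **The 60-participant look is interim.** Its stated uses are to adjust recruitment targets and open moderator analyses. Section 4.5 describes early stopping for lack of efficacy or for safety, not for success.
- **Phase II may not be the confirmatory test.** Section 2.1 says of the minimum of 120 participants that they "will be recruited in Phase II. A statistically powered Phase III study will be designed following completion of Phase II".
- **The wording may be loose.** Maximum likelihood may be meant generically, to include REML.

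A reader might infer a stronger point: that the Phase II tests run at 6–7% and that the primary result fails to hold its stated level. The documents do not support this. A figure near 7% (6.9%) needs both a z reference and a cohort of about 30, and the plan makes separate version analyses optional and gives no cohort sizes. At the planned looks the highest figure in the balanced case is 5.9%, and it falls to 5.6% if 60 means completers.

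The GEE question is likewise conditional: an uncorrected sandwich variance would have a similar small-sample bias, but the plan does not say one will be used.

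The objection does not remove the omission. Under the estimator the plan names, both reference distributions give more than 5%, and the text does not let a reader tell which applies.

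**Conclusion.** The concern holds as a minor point. ML without stated small-sample degrees of freedom gives a nominal 5% test that runs at about 5.4% (t) to 5.9% (z) with 60 analysed and 5.2–5.4% with 120. If the looks count completers and dropouts are retained, the figures are about 5.3–5.6% and 5.1–5.3%. With a z reference, 95% intervals are about 2–4% too narrow at 60 to 120 analysed. A smaller version cohort would be worse, by an amount that depends on its unstated size.

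These figures rest on balanced data, a linear random-slope model and, for the upper ends, an assumed z reference. They do not show that the primary PHQ-8 analysis is invalid, and the change would barely affect the effect size carried forward to Phase III.

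**What to change.** In Section 4.4 (Phase II), replace the clause that names the estimator with wording such as: linear mixed models for continuous outcomes are fitted by restricted maximum likelihood, with Kenward-Roger or Satterthwaite degrees of freedom for tests and 95% intervals, at both looks and in any version cohort. Both parts are needed, since REML with a z reference would still run at about 5.5% with 60 analysed. Limit the sentence to continuous outcomes, because clinical concerns are modelled as a repeated binary outcome. If GEE results are reported, state a small-sample-corrected sandwich variance.

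The cost is a sentence or two of text and a standard software option. No new data are needed, and the model and the missing-at-random assumption do not change. Intervals become about 1–4% wider at 60 to 120 analysed: from 1/0.992 = 1.008 (120, if t would have been used) to 1/0.963 = 1.038 (60, if z would have been used).
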